## **9. DEFINITION OF ANALYSIS SETS**

### **Intent-to-treat Analysis Set**

All participants who were present on a study unit for at least 24 hours during the 12-month study period will be included in the intent-to-treat analysis set. The intent-to-treat participants will be used for all primary, secondary, and other efficacy analyses. All participants will be included in the intent-to-treat analysis set, regardless of what interventions or challenges were given.

### **Safety analysis set**

Participants who received a dose of amoxicillin as a challenge will be included in the safety analysis set related to the safety of the intervention. All other participants will be classified as not having received an intervention with oral challenge to disprove their allergy label, and thus there are no adverse events potentially associated with the control group.

In addition to reporting the safety of the challenge itself, we also intend to compare the incidence of safety events from use of penicillin between the two groups. This analysis will include the intent-to-treat analysis set.

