## **3.0 Inclusion/Exclusion Criteria**

- Inclusion Criteria:
  - For Pilot Study: VUMC patients age 18 or older with a penicillin allergy reported in their chart and are medically stable, currently admitted to ICU.
  - For the RCT: VUMC patients age 18 or older with a penicillin allergy reported in their chart, and are medically stable, currently admitted to stepdown unit or regular floor bed.
- Exclusion Criteria: Patients with a penicillin allergy reported in their chart, but who are currently medically unstable. Patients who are pregnant.

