## 2. PARTICIPANTS AND TREATMENT ARMS

Adult patients admitted to hospital during the 12-month study period who had 24-hour exposure to any of the study units will be included if they are not known to be pregnant. Pregnancy status is based on either documented known pregnancy via ObGyn status or BhCG results that are classified as positive using VUMC laboratory cutoffs.

Participants will be in either the control group or the intervention group, depending on when they presented to the hospital, and which hospital unit they were exposed to. Specifically:

- Control Group: Any patient who did not have a 24-hour exposure to a study unit where the intervention was active but did have at least 24-hour exposure to a control unit. The current standard of care in hospitalized patients with reported penicillin allergy is to do nothing, with all care at the discretion of the primary team. Hence, no intervention will be provided.
- Intervention Group: Any patient who had a 24-hour exposure to a study unit at any time where the intervention was active. The intervention includes systematic identification those with a penicillin allergy, application of a penicillin allergy risk stratification tool, and use of an oral amoxicillin test dose challenge order set for patients who stratify as low risk. The risk stratification tool has been demonstrated retrospectively to have a >99% (95% CI 96.4,99.9) negative predictive value for the presence of penicillin allergy in those who stratify as low risk. Test dose challenges with amoxicillin are a recommended part of routine practice in patients who report allergy but have symptoms that are low risk for true or ongoing allergy. When a unit crosses over and becomes a “live” unit with the intervention, a patient who was already admitted on the unit needs to be present for 24 hours afterward to be considered exposed to the intervention.

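### The challenge safety set is drawn from participants, who need 24 hours on a study unit, so a patient dosed early who leaves before then is not counted

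*SAP*

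**What the plan says.** SAP section 2 covers adults "who had 24-hour exposure to any of the study units will be included if they are not known to be pregnant". Pregnancy is judged from "documented known pregnancy via ObGyn status or BhCG results that are classified as positive using VUMC laboratory cutoffs", with no time stated for the result relative to the challenge. Participants then fall into one of two groups. The intervention group is "Any patient who had a 24-hour exposure to a study unit at any time where the intervention was active". The control group had no such exposure but "did have at least 24-hour exposure to a control unit".

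SAP section 9 defines the intent-to-treat set as "All participants who were present on a study unit for at least 24 hours during the 12-month study period". It adds that every participant belongs to that set whatever challenge was given, and that the set serves all primary, secondary and other efficacy analyses. The safety set is defined in these words: "Participants who received a dose of amoxicillin as a challenge will be included in the safety analysis set". All other participants are classed as not challenged, "thus there are no adverse events potentially associated with the control group". The SAP's Safety Analysis paragraph presents the safety endpoints for the safety set, and the reporting list uses total challenges as the denominator.

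The trial population in Protocol section 3.0 is "currently admitted to stepdown unit or regular floor bed"; ICU patients belong to the pilot.

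**The concern.** A 24-hour exposure rule is sensible for the comparison of label removal, because it fixes who had a fair chance of receiving the intervention. It is a poor condition for a safety rate. A patient can be dosed, react and leave the study units within the first day, and the reaction may be the reason for leaving. Membership of the safety set then depends on something that happens after the dose and may be caused by the outcome being counted.

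The protocol's overall aim in section 2.0 names safety alongside effectiveness and impact. Challenge tolerance and challenge adverse events are also key secondary endpoints 1 and 3. Few reactions are expected in low-risk patients, so one missing event can visibly change the reported rate and its upper confidence limit.

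**Working it through.** **Step 1. Does participant status require 24 hours?** SAP section 2 includes patients on the basis of 24-hour exposure and puts participants into two groups, each needing 24 hours. A patient with less fits neither. The intent-to-treat paragraph closes by placing all participants in a set that itself requires 24 hours. Both routes give the same answer.

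**Step 2. Can a dose precede hour 24?** Nothing in Protocol section 5.0 or SAP sections 1 and 2 delays risk assessment or challenge. Monitoring after the dose is two checks at 30-minute intervals, about one hour. Immediate allergic events are counted within 6 hours of the dose and non-immediate ones within 24 hours (SAP section 3). Dose, reaction and departure can all fall within the first day.

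**Step 3. Who is in and who is out?**
- Dosed at hour 10, then discharged or moved off all study units with no other qualifying stay: out.
- Dosed at hour 10, then moved to another study unit and reaching 24 hours of exposure there: in.
- 24 hours on a control unit before or after the dose, but less than 24 hours on a live unit: classed as control, but still a challenged participant, so in.
- 24 hours on a unit before it goes live, dosed just after, gone within 24 hours: control by the go-live rule, and in.
- Positive BhCG first known after the dose: not settled by the text, and possibly out.

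**Step 4. Are there no control-group events?** Protocol section 5.0 lists direct amoxicillin challenge as an option in the control arm. The 0.5% control rate in the SAP's power section covers label removal or a test dose challenge. The third and fourth cases above add challenged patients classed as control. The SAP statement conflicts with all of these.

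**Step 5. Direction and size.** The plan gives no figure to reproduce: no number of challenges, no reaction rate and no share leaving before 24 hours. The following is illustration only. With N challenges, x reactors, and shares fr of reactors and fn of non-reactors lost:

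reported rate = x(1 − fr) / [x(1 − fr) + (N − x)(1 − fn)]

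Assume N = 200 and x = 2 (1%):
- fr = fn = 5%: 1.9/(1.9 + 188.1) = 1.0%, unchanged.
- fr = 25%, fn = 5%: 1.5/(1.5 + 188.1) = 0.79%.
- fr = 50%, fn = 5%: 1/(1 + 188.1) = 0.53%.
- fr = 100%, fn = 5%: 0%.
- fr = 0, fn = 5%: 2/(2 + 188.1) = 1.05%.
- fr = 0, fn = 25%: 2/(2 + 148.5) = 1.33%.

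At an assumed 4% (x = 8), the first four cases give 4.0%, 3.18%, 2.15% and 0%. The last two give 8/(8 + 182.4) = 4.20% and 8/(8 + 144) = 5.26%.

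If the only reaction is lost, the exact 95% intervals change as follows:
- 100 challenges: 1/100 (0.03 to 5.45%) becomes 0/99 (0 to 3.66%).
- 200 challenges: 1/200 (0.01 to 2.75%) becomes 0/199 (0 to 1.84%).
- 400 challenges: 1/400 (0.01 to 1.38%) becomes 0/399 (0 to 0.92%).

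For scale, if one of 12 units goes live each month starting in month 1, there are 12 + 11 + … + 1 = 78 live unit-months. At the SAP's 10 to 15 labelled patients per unit-month that is 780 to 1,170 labelled patients. The share of them challenged is not given.

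**The case against.** The safety-set sentence contains no 24-hour condition. The intent-to-treat paragraph adds one to the word participants, which would be redundant if the word already carried it. Total challenges is the stated denominator, and Protocol section 4.0 enrols on admission with no minimum stay. It is fair to say that no sentence in the SAP expressly excludes these patients; the omission comes from reading several together. But the closing sentence of the intent-to-treat paragraph points to the narrow meaning, and the denominator is applied inside the safety set. A wider meaning would also leave secondary endpoints 1 and 3 tied to the intent-to-treat set.

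Three further points stand:
- Adverse events on challenge go to the IRB, the safety monitor and NIAID with no 24-hour condition (Protocol section 6.0). An early reaction could be missing from the SAP rate but would not go unreported.
- Several conditions must coincide before a patient is lost, and the documents do not show that any patient is affected.
- Excluding known pregnancy follows the protocol. Only a result that becomes known after the dose is in question.

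A reader might infer more than the documents support. One inference is that the rate must be understated. Equal loss leaves it unchanged, and uneventful patients may be discharged earlier while a reaction prolongs the stay, which would raise it. Another is that a challenged patient reclassified as control disappears from the safety set. That patient remains a participant and is counted. A third is to judge the rate against the figure of under 1% in the best-practice alert. That figure concerns skin-test positivity, not reactions to a challenge.

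**Conclusion.** The concern holds as a gap in the population definition. Followed as written, the SAP omits a challenged patient who leaves all study units without accruing 24 hours on them, and may omit one whose positive BhCG follows the dose. The challenge adverse event rate is therefore conditioned on post-dose events. The direction depends on whether reactors or non-reactors leave early more often, and the size cannot be computed; the rates and losses shown above are assumptions. The statement about no control-group events is contradicted elsewhere in the documents.

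This should be fixed, but it does not threaten the trial's main conclusion. The primary endpoint and its test are untouched, the challenge safety tables are descriptive, and individual events are reported by a separate route.

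**What to change.** - Define the safety set as every patient given an amoxicillin challenge dose on a study unit during the study period, regardless of time on the unit, efficacy group or a pregnancy result that becomes known after the dose. Use the same population for secondary endpoints 1 and 3.
- Report separately the challenged patients who fall outside the intent-to-treat set, with their reactions.
- Replace the statement about the control group with a table of challenges and reactions by unit status, live or control, at the time of dosing.
- Keep the 24-hour and pregnancy rules for the efficacy set.

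The cost is SAP wording and one extra extract of challenge orders from the health record. No new patients or procedures are needed.

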## **5.0 Study Procedures**

Pilot Study: The teams caring for eligible penicillin allergic patients admitted to the ICU will be provided with the study intervention, as described below.

Control Arm: The current standard of care in hospitalized patients with reported penicillin allergy is to do nothing, versus direct challenge with amoxicillin when an allergy history is perceived to be sufficiently low risk, versus obtaining an allergy consultation for help with management, at the discretion of the primary team. Hence, no intervention will be provided.

Intervention Arm: The intervention will provide access to a best-practices alert containing a penicillin allergy risk stratification tool and an oral amoxicillin test dose challenge orderset for patients who stratify as low risk. The risk stratification tool has been demonstrated retrospectively to have a >99% (95% CI 96.4,99.9) negative predictive value for the presence of penicillin allergy in those who stratify as low risk. Test dose challenges are a recommended part of routine practice in patients who report allergy but have symptoms that are low risk for true or ongoing allergy.

Scenario: For patients who qualify for intervention in a unit randomized to intervention, the following best practice alert or a similar alert will be provided to the rounding physician.

"Did you know that 96-99% of patients of patients labeled as allergic to penicillin can safely tolerate these drugs? Use our tool to determine if your patient is low risk (<1% likely to have a positive allergy skin test) and can be considered for a potential challenge with amoxicillin to remove this allergy label. ([Link to tool](#))."

The embedded link will provide an online risk stratification tool that will allow treating physicians to assess if their patient is low risk. For patients who stratify as low risk, information on oral challenges with amoxicillin and the name of an order set that contains the necessary elements for an oral challenge with amoxicillin will be provided (250mg amoxicillin PO x 1 dose, epinephrine at bedside, vital signs at baseline and q 30 minutes x 2.) For patients whose penicillin allergies stratify as higher or highest risk, information will be provided on the management of these penicillin allergies, with or without consultation from the allergy service. **Treatment decisions on whether to act on the provided information will be made by the treating physician and the patient.**

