## **8.0 Statistical Considerations**

Statistical Analysis Plan: Our primary endpoint will be the percentage of patients who had their penicillin allergy label removed prior to discharge, comparing those who received intervention versus controls. We will also assess the number of patients who underwent oral challenge with amoxicillin in both arms. We will assess these outcomes using intention-to-treat analysis, using an adjusted logistic regression model.

Power and Sample Size Considerations: With no intervention, we assume 0.5% of patients have their penicillin allergy label intentionally removed or receive a test dose challenge during current practice in a six month period based upon preliminary data at Vanderbilt. We can power our study to detect a clinically meaningful difference of 20 additional penicillin-allergic patients per 100 having their penicillin allergy label removed using our intervention. Preliminary data suggest that around 100 patients per month are admitted and discharged from the 8N medical unit, and that 15-20% of all patients admitted at Vanderbilt have a penicillin allergy listed in their chart. Hence, approximately 15-20 penicillin allergic patients would be eligible for inclusion in the intervention group per month.

Assuming pessimistically that a minimum of 10% of patients randomized to intervention will have their physician engage with the tool, leading to an allergy label removed, and that 0.1% of patients in the control group will have a penicillin allergy label removed during current practice, 1:1 allocation of participants, an alpha of 0.05, power of 0.8 and a two-sided test of proportions, we will need a minimum of 35 patients per group (70 total) to detect a minimally clinically meaningful 20% increase in penicillin allergy label removals or amoxicillin challenges. Much smaller sample sizes will be needed to see effects if higher engagement and utilization is observed.

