### Power and Sample Size

To power this study, we assumed 0.5% of patients would have their penicillin allergy label intentionally removed or would receive a test dose challenge in the control condition, based on our observation of usual care for a six-month period at the participating units. Preliminary data further suggest that around 100 patients per month are admitted and discharged from each participating medical unit, and that 10-15% of all patients admitted have a penicillin allergy listed in their chart. Hence, approximately 10-15 penicillin allergic patients would be eligible for inclusion in the intervention group, per unit, per month.

Our sample size was selected to detect a clinically meaningful difference of 20 additional penicillin-allergic patients per 100 having their penicillin allergy label removed using our intervention. Assuming pessimistically that a minimum of 10% of patients randomized to intervention will undergo risk stratification leading to an allergy label removed, and that 0.5% of patients in the control group will have a penicillin allergy label removed during current practice, 1:1 allocation of participants, an alpha of 0.05, power of 0.8 and a two-sided test of differences in proportions, we would need a minimum of 35 patients per group (70 total) to detect a minimally clinically meaningful 20% increase in penicillin allergy label removals. Much smaller sample sizes will be needed to see effects if higher engagement

and utilization is observed. By running this study with one year of intervention (12 medical units with one month step lengths), we will greatly exceed the sample size needed for the main analysis, and we will have sufficient data to report on the secondary outcomes with precision.

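### The SAP says the control group has no challenge adverse events, although both documents allow for challenged controls, and it omits the protocol's two-arm comparison of challenge receipt

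*SAP*

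**What the plan says.** **Safety set.** SAP section 9 (Safety analysis set) bases membership on the dose received, not on the arm: "Participants who received a dose of amoxicillin as a challenge will be included in the safety analysis set related to the safety of the intervention". Its next sentence treats everyone else as unchallenged and concludes "thus there are no adverse events potentially associated with the control group". A second paragraph deals separately with events from penicillin use, compared between groups in the intention-to-treat set. The disputed clause can therefore only concern challenge events.

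**Control care.** Protocol 5.0 gives three options under control-arm care, one of them "versus direct challenge with amoxicillin when an allergy history is perceived to be sufficiently low risk". SAP section 2 leaves control care to the primary team's discretion. The SAP power section assumes that "0.5% of patients would have their penicillin allergy label intentionally removed or would receive a test dose challenge in the control condition", and protocol 8.0 has the same composite: "we assume 0.5% of patients have their penicillin allergy label intentionally removed or receive a test dose challenge during current practice".

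**Challenge receipt as an outcome.** Protocol 8.0 states "We will also assess the number of patients who underwent oral challenge with amoxicillin in both arms". The sentence after it assigns this outcome, with the primary endpoint, to an intention-to-treat analysis by adjusted logistic regression. SAP section 3 lists tolerance of a challenge, uptake of risk assessment and challenge adverse events, but not receipt of a challenge. Receipt appears in the SAP's descriptive analysis as a fidelity count over all labelled patients, with no stated split by arm.

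**The concern.** The SAP's conclusion about controls is offered as a consequence of how the safety set is defined, but it does not follow. It needs the further premise that nobody in the control group is challenged, and the documents' own description of control care contradicts that premise.

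Two things are at stake. First, challenge adverse events are to be reported as a proportion of all challenges. A control patient challenged on clinical judgement, without the risk tool, would be counted with patients the tool had classed as low risk, and the text would tell the reader that no such control events exist. Second, challenge receipt is the step between risk assessment and label removal. The protocol promised a comparison of it between arms. The SAP does not carry that out, and its revision log does not mention the change.

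**Working it through.** **Step 1. Can a control patient be challenged?** The documents give three routes.
- Protocol 5.0 names direct challenge as an option in control care.
- The 0.5% rate in both documents counts patients who "would receive a test dose challenge in the control condition" (SAP wording) together with patients whose label is removed.
- Under SAP section 2, a patient with at least 24 hours on a control unit and less than 24 hours on a live unit is a control. A patient already on a unit when it goes live must stay a further 24 hours to count as exposed. If such a patient is challenged and discharged within those hours, the challenge belongs to the control group.

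**Step 2. What happens to that patient under the SAP?** The first sentence on the safety set admits the patient, and the Safety Analysis section counts the event over total challenges. The event is reported, but not attributed to an arm.

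**Step 3. Labelled patients per unit-month.** The SAP power section gives about 100 admissions per unit per month, of whom 10-15% carry a label. 100 x 10-15% = 10-15, which reproduces the SAP's figure.

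**Step 4. Number of controls.** There are 12 units and one-month steps. Assume 12 months with the first unit live in month 1.
- Control unit-months = 0 + 1 + ... + 11 = 66, so labelled controls = 66 x 10-15 = 660-990.
- The SAP introduction mentions a run-in period. If one baseline month is added, control unit-months = 1 + 2 + ... + 12 = 78, giving 780-1,170.

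**Step 5. Expected control challenges.** Expected number = n x rate; probability of at least one = 1 - (1 - rate)^n.

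| Rate | 66 unit-months: expected | P(at least 1) | 78 unit-months: expected | P(at least 1) |
|---|---|---|---|---|
| 0.5% (composite, SAP) | 3.3-4.95 | 0.96-0.99 | 3.9-5.85 | 0.98-1.00 |
| 0.25% (assumed: half are challenges) | 1.65-2.48 | 0.81-0.92 | 1.95-2.93 | 0.86-0.95 |
| 0.1% (assumed) | 0.66-0.99 | 0.48-0.63 | 0.78-1.17 | 0.54-0.69 |

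The first row is a ceiling for usual-care challenges, because 0.5% covers label removal or challenge and the documents do not split it. The 0.1% row has the same size as the protocol's second control rate, "0.1% of patients in the control group will have a penicillin allergy label removed during current practice", but that is a label-removal rate; its use for challenges is an assumption. The short-stay route in Step 1 is not part of the usual-care rate and cannot be quantified from the documents.

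**Step 6. Is the two-arm comparison anywhere in the SAP?** The SAP's secondary analysis applies adjusted logistic regression to binary secondary endpoints, but receipt is not one of them. Tolerance is defined only among those challenged, so it cannot stand in for receipt.

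**The case against.** The best defence is that the clause is loose wording with no effect on the analysis. Much of that stands, and it rules out several stronger readings.

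- *That the SAP discards control challenge events.* It does not. The safety set takes anyone given a challenge dose, and the intention-to-treat set keeps patients whatever challenges were given.
- *That a safety comparison is biased.* The SAP plans no between-arm contrast of challenge events. The planned between-group contrast concerns penicillin treatment, which the clause does not touch.
- *That the trial could not show whether removals came through challenge.* Risk class, challenge receipt, challenge result and label removal are all to be summarised, and a cross-tabulation would show the route. A two-arm odds ratio for receipt would not do so by itself.
- *That control challenges are certain to occur.* At an assumed 0.1%, the chance of seeing none is 0.37-0.52 (66 unit-months).

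It can also be said that the protocol's numbered secondary outcomes do not include challenge receipt, and that a count survives in the SAP. Both are true. But protocol 8.0 assigns the number challenged in both arms to the intention-to-treat model, and the surviving count has no stated arm split. The defence does not rescue the clause itself, which the documents contradict.

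**Conclusion.** The point holds as two reconciliation faults. The SAP's statement about control-group challenge events does not follow from its safety-set rule and conflicts with both documents' account of control care. The modelled two-arm comparison of challenge receipt in protocol 8.0 has no counterpart in the SAP.

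The numbers are small: at most about 3-5 expected usual-care challenges among 660-990 labelled controls (up to about 6 with a baseline month), and about 1 or fewer at an assumed 0.1%. These figures rest on the SAP's admission and label rates, the assumed start of the first unit, and an unsplit composite rate. The contradiction in the text does not depend on them. The primary endpoint and its test are unaffected; what changes is how challenge safety is attributed and whether a promised outcome is compared.

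**What to change.** - In the SAP's safety analysis set, delete only the clause "thus there are no adverse events potentially associated with the control group" and its connecting words. The membership rule can stay.
- Tabulate challenges and challenge adverse events by study group, and by whether the tool classed the patient as low risk before the dose. State that challenges will be identified in the same way in both groups. The SAP names a smart phrase for documenting tolerance but does not say how usual-care challenges will be found.
- Add receipt of an amoxicillin challenge before discharge (yes or no), among all patients with a label, as a two-arm intention-to-treat comparison in line with protocol 8.0. Report counts and a risk difference with a confidence interval beside the adjusted model. With few control events the model may be unstable, and with none the odds ratio has no finite estimate.

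The cost is a change of wording, one more analysis on data already planned for collection, and review of a handful of charts. No clinical procedure changes.
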